Title: Modulation of Sensory Acuity With Transcranial Magnetic Stimulation (TMS) (Exp 7)

NCT number: NCT05723575

Document date: 7/18/2024

Study Protocol

This study consists of three related behavioral paradigms aiming to test sensorimotor adaptation, a correlative analysis investigating the relationship between the outcome measurements from these three experiments, and several experiments seeking to modulate these outcome measures. Here we describe Experiment 7, which used transcranial magnetic stimulation (TMS) to modulate somatosensory acuity of the tongue.

Experiment 7 specific Methods: Participants will complete three TMS sessions (iTBS, cTBS, sham) and a fourth behavioral-only control session. Each session will be separated by at least one week with the order counterbalanced across participants. The target of the stimulation is left primary somatosensory cortex (S1). The duration of tbTMS stimulation is short (40-190s), with effects that begin ~5 minutes following stimulation and persist for up to 30 minutes. In each TMS session, sensory acuity will be tested in two tasks (spatial and temporal) before and after application of theta-burst TMS (tbTMS):

- *Task practice:* Participants first complete a brief training to familiarize them with each acuity task and to ensure they met performance criteria (five consecutive correct responses).
- *Baseline tests:* Participants complete 3 blocks of each task, with the tasks alternating.
- *TMS localization and thresholding:* Single-pulse TMS is used to localize the target stimulation site (S1) and determine the active motor threshold. S1 is localized on each participant's brain surface with Brainsight neural navigation by moving the stimulator 2 cm posterior to a motor hotspot that elicits tongue motor-evoked potentials (MEPs).
- *Rest:* 20-minute break to allow the somatosensory cortex to recover from any potential disruption related to single-pulse TMS.
- *TBS:* Delivery of TBS to S1. Stimulation intensity will be set to 80% of the active motor threshold. Sham stimulation will be applied with the coil rotated away from the head (coil facing downward). This emits the same sound as active stimulation without stimulating the brain.
- *Post tests:* Performed every 5 minutes for 45 minutes following stimulation: participants complete 10 blocks of each task (SDT and TDT), alternating between the tasks with a 1-minute break in between each task.

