In the 4th behavioral-only session ("control"), participants' acuity is tested without TMS localization.

- *Somatosensory acuity metrics:* The acuity tasks measure tactile acuity (spatial amplitude and temporal order judgment) with a custom corticalmetrics Brain Gauge vibrotactile stimulator. These measures reliably track the recovery of somatosensory function after neurological damage and can be modified with tbTMS. We use tactile acuity as a proxy for full somatosensation, given the difficulty in measuring proprioception in the oral system. Tactile acuity has been suggested to be important for speech production, as tactile contact is maintained parasagittally during vowel production and tactile deprivation leads to imprecise speech movements.
- *Data analysis and outcome measurements:* Each acuity task (spatial amplitude and temporal order judgment) yields a threshold (spatial amplitude discrimination threshold in μ m; temporal discrimination threshold in ms) representing the smallest difference detectable by the participant at a given time point. For each acuity task, we will compare the change in threshold from pre- to post-TMS. Post-TMS values will be normalized by subtracting baseline thresholds for each task on a session-specific basis, then compared across time windows.

- *Sample size with power analysis:* Given previous results in the hand ($d = 1.8-3.1$), we conservatively anticipate an effect size of Cohen's $d = 1$. Testing 17 participants gives a power of .82 with $\alpha = 0.05$.

Statistical Analysis Plan

Experiment 7: We will compare the change in sensory acuity from pre- to post-TMS between sessions using a repeated measures ANOVA. Post-TMS values will be normalized by subtracting baseline thresholds for each task on a session-specific basis, then compared across time windows. To compare changes in thresholds across sessions, a single repeated-measures ANOVA will be conducted for each task with sessions (cTBS, iTBS, control, sham) and time windows as independent variables.

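### The SAP names no active-versus-sham contrast, so its four-session ANOVA can give a significant session main effect because control alone differs, with no theta-burst effect

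*Combined protocol and SAP*

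**What the plan says.** The Study Protocol states that Experiment 7 "used transcranial magnetic stimulation (TMS) to modulate somatosensory acuity of the tongue". There are three TMS sessions (iTBS, cTBS, sham) and a fourth, behavioral-only control session.

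- **Sham.** The coil is rotated away from the head: "This emits the same sound as active stimulation without stimulating the brain". Sham is one of the three TMS sessions, for which the Methods list localization and thresholding between the baseline tests and the post-tests.
- **Control.** In this session "acuity is tested without TMS localization".
- **Rest.** The TMS sessions include a "20-minute break to allow the somatosensory cortex to recover from any potential disruption related to single-pulse TMS".
- **Post-tests.** There are 10 blocks per task: "Performed every 5 minutes for 45 minutes following stimulation".
- **Outcome.** Thresholds have the session's own baseline subtracted. The protocol adds: "For each acuity task, we will compare the change in threshold from pre- to post-TMS". It names no comparator.
- **Inference.** The SAP states that "a single repeated-measures ANOVA will be conducted for each task with sessions (cTBS, iTBS, control, sham) and time windows as independent variables".
- **Power.** "Testing 17 participants gives a power of .82" at alpha 0.05 with Cohen's d = 1. The comparison to which d refers is not given.

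Neither the protocol nor the SAP names a planned contrast, a follow-up test or a multiplicity rule, or says which pattern of session differences would count as a theta-burst effect.

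**The concern.** The trial asks whether theta-burst stimulation changes tongue acuity. Sham is the natural comparator, because it shares the procedure and the sound and omits the stimulation of the brain. The planned session test instead asks whether four sessions have equal mean change, and control enters on the same footing as the rest.

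Control differs from the other three by more than theta-burst stimulation, since it skips localization. That step falls between baseline and post-tests, so subtracting the session's baseline cannot remove any effect it has on the change score. Counterbalancing deals with session order and does not touch this procedural difference. The protocol itself takes single-pulse disruption seriously enough to schedule a rest, but the plan does not check that the rest was sufficient.

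A significant session effect could therefore come from control alone. Someone then has to choose a comparison to explain it. Four sessions allow 4 × 3 / 2 = 6 pairwise comparisons per task, and there are 10 post-test blocks. With nothing named, comparator and window could both be chosen after seeing the data.

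**Working it through.** **Inputs from the documents.** n = 17; four sessions; alpha 0.05 (taken as two-sided); d = 1; stated power .82.

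**Assumptions.** Compound symmetry across sessions, and the size of any control-only shift. The documents give neither.

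**1. The stated power.** An unpaired comparison with 17 per group and d = 1 gives 0.807 (t) or 0.830 (normal approximation), so .82 is reproduced approximately. A paired t-test with standardized paired effect dz = 1 and n = 17 gives 0.972. The stated figure therefore does not show which comparison was powered.

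**2. Session main effect when only control shifts.** Let the shift be s paired SDs. With within-session SD σ and between-session correlation ρ, the paired SD is σ√(2(1−ρ)). The noncentrality is λ = n Σ(μ_j − μ̄)² / (σ²(1−ρ)). One session of four displaced by δ gives Σ(μ_j − μ̄)² = 0.75 δ², and δ² = 2(1−ρ)σ²s². So λ = 17 × 1.5 × s² = 25.5 s², on 3 and 48 df (critical F 2.80).

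| s | λ | P(session effect significant) |
|---|---|---|
| 0 | 0 | 0.050 |
| 0.1 | 0.255 | 0.064 |
| 0.25 | 1.594 | 0.151 |
| 0.5 | 6.375 | 0.509 |
| 0.75 | 14.344 | 0.877 |

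The formula does not depend on which session is displaced, so a cTBS-only effect of the same size gives the same figures. Simulation (200,000 trials) agrees: at s = 0.5, 0.509 for control-only and 0.510 for cTBS-only.

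If the shift is instead expressed in raw SDs of the change score, a 0.5 SD shift gives 0.27, 0.51 and 0.75 at between-session correlations of 0, 0.5 and 0.7.

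**3. Active-versus-sham contrasts on the same data.** Probability that at least one of iTBS-sham and cTBS-sham rejects, Holm over the two:

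| s | Control-only shift | cTBS-only effect |
|---|---|---|
| 0.1 | 0.047 | 0.057 |
| 0.25 | 0.047 | 0.119 |
| 0.5 | 0.047 | 0.380 |
| 0.75 | 0.047 | 0.735 |

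The contrasts ignore control and respond to the stimulation effect.

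**4. Session-by-window term.** A control shift that is constant over time does not move it. In simulation (17 × 4 × 10, AR(1) 0.5, no sphericity correction) rejection stays at 0.077–0.082 for shifts of 0 to 0.75, with no trend; the excess over 0.05 is non-sphericity. A control-only shift that fades linearly to zero (mean 0.5) raises it to 0.288 uncorrected. With Greenhouse-Geisser correction a repeat gave 0.098 against a null rate of 0.011. The plan specifies no correction.

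**5. Power of a named contrast.** Paired t, n = 17; alpha 0.025 is the strictest Holm step for two contrasts.

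| Reading of the power statement | dz | Power at 0.05 | Power at 0.025 | n for 80% at 0.025 |
|---|---|---|---|---|
| d = 1 is the paired effect | 1.000 | 0.972 | 0.939 | 17 is enough |
| .82 is the paired power | 0.743 | 0.820 | 0.718 | 20 |
| d = 1 on the raw SD, correlation 0 | 1/√2 = 0.707 | 0.781 | 0.671 | 22 |

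**The case against.** The symmetry in step 2 holds for any four-level omnibus test. Following a significant omnibus result with pairwise tests is common practice, and sham is already in the model, so the right comparison is available. The plan does not say that it will read a significant session effect as a theta-burst effect.

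No figure in the documents suggests that control will differ from sham, and the rest period is there to limit one such difference. The striking percentages come from the larger assumed shifts; at 0.1 and 0.25 they are 6% and 15%. The protocol expects effects from about 5 to 30 minutes within 45 minutes of testing, so the session-by-window term matters at least as much as the main effect, and a constant control shift leaves it alone.

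Most of this is fair and limits the claim. The shift is hypothetical, and the percentages describe the session main effect only. Two things still stand. No follow-up comparison is written down, so its availability does not settle which one will be used. And a significant interaction is no more specific than the main effect about which session produced it; the fading-shift case shows that control can drive it too, though the amount depends heavily on the sphericity correction.

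**Conclusion.** The concern holds. The plan's only stated test cannot by itself attribute a session difference to theta-burst stimulation, and the comparison that could do so is not prespecified. This follows from the design and needs no assumption about control.

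How often it would mislead does rest on assumption: about 6% to 88% significant session effects for control-only shifts of 0.1 to 0.75 paired SDs, under compound symmetry with n = 17. Those are correct rejections of equality among four sessions and should not be called type I errors; they simply do not answer the trial's question. It is a worthwhile, inexpensive improvement to the SAP and does not invalidate the design.

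**What to change.** Amend the SAP as follows, within the planned model for each task:

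1. Prespecify iTBS versus sham and cTBS versus sham as the primary contrasts on baseline-subtracted thresholds.
2. Apply Holm adjustment over the two contrasts.
3. State which of the 10 post-test blocks the contrasts use.
4. Report sham versus control separately, as a check on the effect of the procedure.
5. Keep the four-session ANOVA as supporting analysis.
6. If outcome data have already been examined, label the contrasts as specified afterwards.

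No new session or measurement is needed. The cost is the stricter alpha, with power at n = 17 ranging from 0.94 down to 0.67 across the readings in step 5 of the working. The SAP should therefore also say which comparison d = 1 refers to. Holm over two contrasts controls error within a task; if a claim is to be made across both tasks jointly, the SAP needs a further rule for that.
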